6.0 Sites, Programs, Resources, and External IRB Review

6.1 * UCSF AND AFFILIATED SITES (check all that apply): (REQUIRED)

- UCSF Benioff Children's Hospital Oakland (BCHO)
- UCSF Cancer Center Berkeley
- UCSF Cancer Center San Mateo
- UCSF China Basin clinics and facilities
- UCSF Helen Diller Family Comprehensive Cancer Center
- UCSF Langley Porter Psychiatric Institute (LPPI)
- UCSF Medical Center at Mission Bay (Benioff Children's Hospital, the Betty Irene Moore Women's Hospital, Bakar Cancer Hospital, or outpatient clinics)
- UCSF Mount Zion
- UCSF Parnassus (Moffitt-Long hospital, dental clinics or other outpatient clinics)
- UCSF Other Sites (including Laurel Heights and all the other sites outside the main hospitals and clinics)
- Fresno - UCSF Fresno OR Community Medical Center (CMC)
- Gladstone Institutes
- Institute on Aging (IOA)
- Jewish Home
- SF Dept of Public Health (DPH)
- SF VA Medical Center (SF VAMC)
- Vitalant (formerly Blood Centers of the Pacific and Blood Systems Research Institute)
- Zuckerberg San Francisco General (ZSFG)

Research involving the SFDPH: SFDPH sites and clinics has some special requirements, including adherence to the [SFDPH HIPAA Policy](#), involvement of an [SFDPH-approved investigator](#), and inclusion of a signed [SFDPH Research Proposal Approval](#). Your submission will be returned to you if it does not include this form.

6.2 LOCATIONS: At what locations will study visits and activities occur:

Study visits will occur at [name]

6.3 OFF-SITE PROCEDURES: Will any study procedures or tests be conducted off-site by non-UCSF personnel:

Yes No

Please identify which procedures may be done off-site:

Study activities will take place at [name]. These activities include screening, enrollment, and follow-up visits that include survey administration, urine tests, safety labs, sweat patches and HIV tests.

6.4 RESEARCH PROGRAMS: Check any UCSF research programs this study is associated with:

- Cancer Center
- Center for AIDS Prevention Sciences (CAPS)
- Global Health Sciences
- Immune Tolerance Network (ITN)
- Neurosciences Clinical Research Unit (NCRU)
- Osher Center
- Positive Health Program

6.5 * CTSI CRS SERVICES: (REQUIRED) Will this study be carried out at one of the UCSF Clinical Research Services (CRS) units or utilize CRS services:

Yes No

6.6 * MULTI-CENTER TRIAL: (REQUIRED) Is this a multi-center or multi-site research trial:

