- Use of placebo
- Biopsy conducted solely for research purposes
- Sham surgical procedure
- None of the above

8.9 * PROCEDURES / METHODS: (REQUIRED)

For clinical research, list all study procedures, tests and treatments required for this study, including when and how often they will be performed. If there are no clinical procedures, describe the research activities.

If some of the activities would occur even if the person were not in the study, as in the case of treatment or tests performed for diagnostic purposes, **clearly differentiate between those activities that will be done solely for research purposes and those that are happening as part of routine care.**

Examples may include:

- additional scans outside standard clinical diagnosis or monitoring
- additional biopsies to collect tissue for research
- extra clinic visits
- extra lab tests not required for clinical care

If you have a procedure table, attach it to the submission with your other study documents.

Study Procedures: Potential participants will be asked brief eligibility screening questions in person or over the phone after providing verbal consent. Potential participants will provide informed consent and be screened for eligibility during the pre-enrollment screening visit. The schedule for the study procedures is shown in **Table 3**.

Participants will be compensated for their time at each visit and in responding to daily ecological momentary messages (up to a total of \$421). Participants will receive \$50 for the 2 in-office screening visits (\$20 at Screen 1 and \$30 at Screen 2), \$15 each for in-office run-in visits 1 and 2, \$40 for in-office enrollment, \$15 for remote weekly visits (1-3, 5-7, and 9-11), \$15 for in-office weekly visits (4, 8, 12), \$40 for in-office week 4 (month 1) and week 8 (month 2) visits, and \$50 for week 12 (month 3). In addition, they will receive \$0.40 for each day that they complete the daily EMA series throughout the 12-week treatment period (up to \$36). Participants will be paid by cash, visa gift cards, or by paypal.

Participants could receive a gift card (\$10) for partial screening visits. For any snowball referral that has completed a screening visit, the participant who referred the new participant will receive

\$10. If the new participant enrolls in the study, the participant who referred the new participant will receive \$40.

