Sweat Testing: We will utilize tamper evident sweat patches (PharmChem, Inc., Fort Worth, Texas) that absorb perspiration 24 hours a day, for up to 10 days of continuous wear.¹⁸⁷ These patches will be tested for the presence of meth and meth metabolites, using testing procedures approved by the FDA since 1995.¹⁸⁷ PharmChek patch enzyme immunoassays to detect meth in sweat have been found to have 85% sensitivity and a 93% specificity rates, compared to gas chromatography-mass spectrometry.¹⁸⁸ At screening visits, we will affix patches on all participants. These patches have a semi-permeable membrane to allow oxygen, carbon dioxide and water vapor to pass through the patch, keeping the skin underneath sterile and healthy. We will replace the used patch worn since the prior visit and send those used patches for meth testing to PharmChem's laboratories. These patches will retain meth and meth metabolites for any use during the period it was worn. Hence, we anticipate no gaps in the window of detection for meth use.

PrEP and ART adherence: Among HIV-negative participants on PrEP and HIV-positive participants on ART, we will collect 20 ml. urine samples and test drug levels using a Urine Tenofovir immunoassay and RNA viral load from blood samples collected at baseline and monthly follow-up visits. For PrEP, good adherence will be defined as having tenofovir-diphosphate (TFV-DP) concentration of 1500 ng/ml, which has been classified as evidence of consistent dosing.^{182,183 184} Good ART adherence among participants living with HIV will be defined as having undetectable HIV viral load below 50 copies/ml.

Study drug adherence: The study will collect self-reported adherence via weekly modified TLFB assessments, similar to prior targeted naltrexone studies^{106,209} and via EMA for all participants.¹⁰⁹ Pill counts at weekly visits will also assess adherence. **MEMS caps** will be used to track medication adherence daily for as-treated analyses; each cap opening is recorded as an event in real time. MEMS have been shown to be reliable for adherence monitoring and have been used in our studies.^{66,124 109}

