For the safety to participants and staff during COVID-19, the study has been designed with hybrid visits according to Interim UCSF research guidelines. The weekly visits (weeks 1, 2, 3, 5, 6, 7, 9, 10 and 11) will be conducted remotely through zoom. The participant will be given single M-AMP urine test kits and urine collection bottles at the in-office visits and trained how to conduct the urine test. The participant is asked to provide a urine sample in the urine collection bottle before the video visit. The participant will dip the M-AMP stick in the urine during the video visit and the dip stick will be shown to the counselor. Due to video resolution, a faint red line may not be able to be viewed by video. If this happens, the participant will be asked to take a picture of the dip stick and upload it to a secure portal or an encrypted e-mail. After IRB approval, we will test this option on RedCAP through the participant survey invitation and embedded image upload option.

13.5 * BENEFITS: (REQUIRED) Note: These are the benefits that the IRB will consider during their review. They are not necessarily appropriate to include in the consent form.

Possible immediate and/or direct benefits to participants and society at large (check all that apply):

Positive health outcome (e.g. improvement of condition, relief of pain, increased mobility, etc.)

Closer follow-up than standard care may lead to improved outcomes or patient engagement

Health and lifestyle changes may occur as a result of participation

Knowledge may be gained about their health and health conditions

Feeling of contribution to knowledge in the health or social sciences field

The research presents a reasonable opportunity to further the understanding, prevention, or alleviation of a serious problem affecting the health or welfare of children

Other benefit (describe below)

None

Briefly discuss the other possible benefits:

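### The claim that sweat patches leave no gaps in meth detection cannot hold during the 12-week treatment period under the hybrid visit schedule as written

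*Protocol*

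**What the plan says.** Protocol section 8.9 (Sweat Testing) describes tamper-evident patches that "absorb perspiration 24 hours a day, for up to 10 days of continuous wear". On application it says: "At screening visits, we will affix patches on all participants". On changing them it says: "We will replace the used patch worn since the prior visit and send those used patches for meth testing to PharmChem's laboratories". From this it concludes: "Hence, we anticipate no gaps in the window of detection for meth use".

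The visit schedule is set elsewhere. Section 13.4 states: "The weekly visits (weeks 1, 2, 3, 5, 6, 7, 9, 10 and 11) will be conducted remotely through zoom". Section 15.4 repeats this, and the COVID-19 paragraph of section 8.9 lists the same weeks. The payment paragraph of section 8.9 names weeks 4, 8 and 12 as the in-office follow-up visits. It also makes the two screening visits, the two run-in visits and enrollment in-office.

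The remote procedure in sections 13.4 and 15.4 is a urine dipstick that the participant runs on video, with a photograph if the line is faint. It has no patch step.

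Section 6.3 lists patches among site activities, in the words "follow-up visits that include survey administration, urine tests, safety labs, sweat patches and HIV tests". That is the tail of one list covering screening, enrollment and follow-up together. Section 9.1 says patches will be collected. Tables 3 and 4 have no patch row. Table 4 and the SAP make weekly urine the Aim 1 outcome. Section 8.13, however, expresses its Aim 1 detectable difference (about 14.5 points) as patch positivity, and the Aim 1 heading in section 11.3 names patch tests.

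**The concern.** Detection without gaps needs each patch to be replaced before its wear time runs out, so changes can be no more than 10 days apart. Weekly in-person visits would achieve this. The hybrid schedule as written does not, because the in-office follow-up visits are 28 days apart. The sentence appears not to have been reconciled with that schedule.

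The stake is how any follow-up patch result would be read. A week-4 patch described as worn since the prior visit would either have been on for 28 days, well past its stated limit, or have covered at most 10 of those days. Reported without wear dates, it would look like continuous monitoring. No schedule tells staff when to change patches or tells the analyst which days a result represents.

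**Working it through.** **Inputs**
- Patch wear time L = 10 days (section 8.9, Sweat Testing).
- In-office visits from enrollment on: weeks 0, 4, 8 and 12 (section 8.9, payment paragraph), so the interval between them is I = 28 days.
- Treatment period: 12 weeks = 84 days (section 8.3), or three intervals.
- Patch change at remote visits: none described (sections 13.4 and 15.4).

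**The plan's own figure.** The stated gap is zero. The uncovered share of an interval is max(0, I − L) / I.
- Changes every 7 days: max(0, 7 − 10) / 7 = 0. The plan's statement is reproduced.
- Changes every 14 days: (14 − 10) / 14 = 28.6%.
- Changes every 28 days: (28 − 10) / 28 = 18/28 = 64.3%.

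The statement therefore holds with weekly in-person changes and fails with changes at the listed in-office visits.

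**Whole treatment period, patches changed only in the office.** Covered: at most 3 × 10 = 30 days. Uncovered: at least 84 − 30 = 54 days, and 54/84 = 64.3%. A patch left on for the whole interval would be worn 28/10 = 2.8 times its stated limit.

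**Whole treatment period, patches for screening only.** No patch is applied during treatment, so follow-up patch coverage is zero.

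**Sensitivity to wear time (assumed values, not in the documents).** At 28-day intervals, a 7-day life gives 21/28 = 75% uncovered and a 14-day life gives 14/28 = 50%.

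**Counting weekly urine as well.** The documents give no urine detection window, so w is assumed to be 1 to 5 days before each weekly test. In each 28-day interval the patch covers days 0 to 10, so the day-7 urine test adds nothing. The tests at days 14, 21 and 28 each add w days, for w up to 4.
- w = 1: (18 − 3) / 28 = 53.6% uncovered by either test.
- w = 4: (18 − 12) / 28 = 21.4%.
- w = 5: the day-14 window overlaps the patch by one day, so (18 − 4 − 5 − 5) / 28 = 14.3%.

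Urine narrows the gap in overall detection but does not close it anywhere in this range.

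**The case against.** The strongest reply is that the sentence was never about the treatment period. Section 8.9 mentions affixing patches only at screening. The screening, run-in and enrollment visits are all in-office, and patch wear could be continuous across them if they are no more than 10 days apart; their spacing is not given. Tables 3 and 4 schedule no follow-up patch, and the list in section 6.3 pools three visit types. A reader might infer from section 6.3 that patches are assigned to follow-up, but the full sentence does not establish that. This part of the reply stands, and it makes the 64% conditional. It does not rescue the sentence, which carries no limit to screening, follows a rule about serial replacement, and sits in a protocol where sections 8.13 and 11.3 carry the patch into Aim 1.

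Second, staff-only changing is inferred from the text's wording and from silence about remote changes. A home-change or mail-in procedure would close the gap, but none is described. Section 8.9 also presents remote visits as a COVID-19 precaution open to revision. Section 12.14 counts weekly visits as site time: its 930 to 1305 minutes is reproduced by two screening, one enrollment, nine weekly and five monthly or post-treatment visits (120 + 90 + 270 + 450 = 930; 180 + 120 + 405 + 600 = 1305). That is a real tension, but sections 8.9, 13.4 and 15.4 are explicit that those visits are remote.

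Third, the consequence is limited. A reader might infer that the primary analysis is compromised, or that negative patches would be used to claim a month of abstinence. The documents support neither. The SAP does not mention patches, urine is the stated gold standard against self-report, and no abstinence endpoint is defined.

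**Conclusion.** The statement cannot hold for the 12-week treatment period under the schedule as written. If patches are worn in follow-up and changed only at in-office visits, at least 54 of 84 days (64%) have no valid patch coverage. If patches are for screening only, none of the 84 days has any. The contradiction between a 10-day wear time and 28-day in-office intervals needs no outside figure. The 64% rests on two assumptions that the documents leave open: that patches are worn in follow-up, and that only staff change them at office visits. It should be quoted with that condition and not as an established fact about follow-up.

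The figure concerns the patch alone. The primary analysis rests on weekly urine and is unaffected. This is a point to correct in the protocol text, made somewhat more important by the patch wording that remains in Aim 1.

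**What to change.** 1. **Section 8.9, Sweat Testing.** Delete the concluding sentence, or limit it to pairs of in-office visits no more than 10 days apart (screening, run-in and enrollment, where spacing allows). State that each patch result applies only to the days the patch was worn, and that a patch worn beyond 10 days is not evaluable.
2. **Section 6.3.** Split the pooled list by visit type. Keep patches at screening, where inclusion criterion 5 relies on them, and do not list them for follow-up. Alternatively, if follow-up patches are wanted, add a patch row to Tables 3 and 4 and a remote-change procedure that respects the 10-day limit.
3. **Sections 8.13 and 11.3, Aim 1.** Replace the patch wording with urine, to match Table 4 and the SAP. In section 8.13 a change of word alone is not enough. It would leave about 14.5 points at 80% retention there, against about 24 points at 90% retention in section 11.3 and the SAP, so these figures must be reconciled at the same time.

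The cost is protocol wording only; the urine endpoint and the sample size do not change. Dropping follow-up patches gives up data that could not be read as continuous coverage and saves patch and laboratory cost. Keeping them means writing and running the remote-change procedure.
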